Prospective Case Series on a Combination Methylene Blue, Gentian Violet, and Ovine Forestomachderived Extracellular Matrix Dressing for Hidradenitis Suppurativa

NCT04354012

IRB Approval Date: 6/14/2021

Study Title: Prospective case series on the use of methylene blue, gentian violet, and ovine forestomach-derived extracellular matrix wound dressings for Hidradenitis Suppurativa

Principal Investigator: [name]

Sponsor or funding source: Departmental (dressings provided by Appulse Medical)

Background, Rationale and Context

Hidradenitis suppurativa (HS) is a chronic and debilitating inflammatory disease most frequently affecting the axilla, groin, and inframammary regions. Symptoms include nodules, abscesses, sinus tract formation, malodorous drainage, and scarring. These symptoms interfere with everyday activities, which can lead to social embarrassment and isolation. Patients with HS suffer psychological effects, such as increased levels of anxiety, depression, and loneliness, which impair quality of life. 3,4

Patients suffer with the burden of at home wound care for recurrent, draining nodules. Persistent lesions affect patients' lives by limiting their daily activities. Currently, patients are instructed to use gauze and tape to cover draining wounds, but this can be insufficient and difficult due to the nature and location of lesions associated with HS. Patients suffer with caring for their wounds, which can lead to frustration. Providing patients with a standard wound care regimen to take home can improve patients' quality of life and control of their disease. General recommendations for wound care in HS patients are limited. Improvements in the standard of care for wound management in HS are needed to aid patients.⁵

Objective

The objective of this case series is to monitor time and outcome of healing of wounds associated with HS using Endoform [ovine forestomach], Hydrofera Blue [methylene blue and gentian violet], and Hypafix tape.

Methods and Measures

Design

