This will be a single-center, case series evaluating the length of time wound healing occurs using methylene blue, gentian violet, and ovine forestomach wound dressings to HS lesions. Patients of Wake Forest Dermatology clinic with a diagnosis of HS with draining nodules and open wounds will be recruited in clinic. Participants will be provided with methylene blue, gentian violet, and ovine forestomach products at screening/baseline visit. Lesions will be measured and recorded. Participants will complete a Numerical Rating Scale of Patient Reported Pain (NRS/Appendix I). Upon enrollment, participants will be provided with a standard cleansing protocol to be followed at home including using antibacterial soap prior to applying wound dressings. Dressings are to be changed every 3 days. In addition, they will be instructed to avoid bleach baths or acidic products for the duration of their involvement in the study. After visit 1, participants will return for follow-up at week 1, week 2, week 4, and week 8. At each visit, wounds will be measured and photographed, NRS will be completed, and participants will be provided with wound dressing products as needed.

Setting

Wake Forest Baptist Health Department of Dermatology Clinic during scheduled follow-up appointments. All study procedures will occur in-person.

Subjects selection criteria

• Inclusion Criteria

Protocol version:

Template updated 9.24.14

- o Individuals with hidradenitis suppurativa with non-healing wounds or draining abscesses/nodules
- o Individuals over 18 years of age

• Exclusion Criteria

- o Individuals younger than 18 years of age
- o Individuals without a diagnosis of HS

• Sample Size

 10 participants will be provided with wound care dressings from Appulse Medical.

Interventions and Interactions

Methylene blue, gentian violet, and ovine forestomach wound dressings will be provided by Appulse Medical. These wound care products are used for local management of wounds. This study is monitoring the impact these wound care products have on wounds associated with HS. Additionally, NRS assessments will be administered to evaluate the impact wound healing has on patient reported pain.

Endoform (ovine forestomach) is a natural dermal template used in all phases of wound healing. This product helps to stabilize, build, and organize tissue in acute and chronic wounds.

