Hydrofera Blue is an antibacterial foam dressing that contains methylene blue and gentian violet to manage wounds. This is a safe, non-cytotoxic product that can be worn for 7 days while not inhibiting growth factors. This products wicks bacteria into the foam and away from the wound surface using natural negative pressure through capillary flow.

Hypafix tape aids in stabilization of wound dressings. This product is easy to apply, skin friendly, and comfortable to use.

Screening Visit/Visit 1

- Informed consent will be obtained
- Photographs of wounds at baseline will be taken
- Wounds will be measured, and appropriate amount of wound dressings will be administered and application instructions will be provided
 - o Clean the wound with antibacterial soap.
 - Apply Endoform dermal template first, trimming it to fit the lesion, followed by Hydrofera Blue and fixed using Hypafix tape.
- Basic demographics, BMI, and smoking history will be recorded
- Participants will receive a standardized cleansing regimen to follow at home (Appendix II)
- Completion of NRS
- Completion of Dermatology Life Quality Index (DLQI/Appendix III)
- Completion of Sartorius Hidradenitis Suppurativa Score (Appendix IV)

Visits 2, 3, 4, 5

- Photographs of wounds at baseline will be taken
- Previous and new wounds will be measured, and appropriate amount of wound dressings will be administered
- Completion of NRS
- Completion of DLQI
- Completion of Sartorius Hidradenitis Suppurativa Score

Outcome Measure(s)

- 1. Assess the time for wound healing to occur using Endoform and Hydrofera Blue products.
- 2. Asses the percent healing that occurs over 8 weeks of follow-up using Endoform and Hydrofera Blue products.
- 3. Assess changes in patient reported pain via NRS
- 4. Assess changes in Sartorius scale

Analytical Plan

Wound area will be calculated by measuring length multiplied by width of the lesions. Wounds will be measured at each visit, and percent (%) change in area of lesion will be recorded.

Time versus % area healed will be analyzed. Post hoc analyses will be conducted to explore the relationship between participants' self-report on psychosocial measures and wound healing time.

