Results will be analyzed initially using descriptive statistics. Comparison between groups will be done using chi square tests for proportions, and t-tests or ANOVA procedures for continuous variables. Regression analysis will be performed to identify independent outcome predictors. Other inferential statistical analysis will be conducted as appropriate.

Human Subjects Protection

All information provided will be kept confidential. Subjects will remain deidentified.

Subject Recruitment Methods

Subjects who meet the inclusion and exclusion criteria will be eligible for participation in this study. Participants will be recruited from the Wake Forest Department of Dermatology clinic by either the PI or members of the study team.

Informed Consent

Written informed consent will be obtained by members of the study team. The risk of harm or discomfort that may occur as a result of taking part in this research study is not expected to be more than in daily life or from routine physical or psychological examinations or tests. The rights and welfare of study will be protected through the use of measures to maintain the confidentiality of study information. Study results will be presented or published in lieu of providing individual subjects additional information regarding the study.

Confidentiality and Privacy

Confidentiality will be protected by collecting only information needed to assess study outcomes, minimizing to the fullest extent possible the collection of any information that could directly identify subjects, and maintaining all study information in a secure manner. To help ensure subject privacy and confidentiality, only a unique study identifier will appear on the data collection form. Any collected patient identifying information corresponding to the unique study identifier will be maintained on a linkage file, store separately from the data. The linkage file will be kept secure, with access limited to designated study personnel. Following data collection subject identifying information will be destroyed 3 years, consistent with data validation and study design, producing an anonymous analytical data set. Data access will be limited to study staff. Data and records will be kept locked and secured, with any computer

data password protected. No reference to any individual participant will appear in reports, presentations, or publications that may arise from the study.

Data and Safety Monitoring

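### The named between-group tests do not fit a one-group case series of 10 people, and no within-person method is pre-specified for the changes in NRS pain and Sartorius score

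*Combined protocol and SAP*

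**What the plan says.** The Objective describes monitoring: "The objective of this case series is to monitor time and outcome of healing of wounds associated with HS". Under Design: "This will be a single-center, case series evaluating the length of time wound healing occurs". Sample Size gives a single set of people: "10 participants will be provided with wound care dressings from Appulse Medical". The visit schedule is repeated measurement of those people: "After visit 1, participants will return for follow-up at week 1, week 2, week 4, and week 8". No control, second dressing or other comparison arm appears.

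Outcome Measure(s), items 3 and 4, are changes in NRS pain and in the Sartorius scale. Both instruments are completed at all five visits.

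The Analytical Plan opens its statistical paragraph with "Results will be analyzed initially using descriptive statistics" and continues with "Comparison between groups will be done using chi square tests for proportions, and t-tests or ANOVA procedures for continuous variables". It then announces a regression for outcome predictors and closes with "Other inferential statistical analysis will be conducted as appropriate". Elsewhere in the same section it says that time will be analysed against percent area healed, without naming a method. These between-group procedures are the only tests named.

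On wounds, the schedule for Visits 2 to 5 says: "Previous and new wounds will be measured, and appropriate amount of wound dressings will be administered". The Analytical Plan records percent change in area for each lesion. It does not say against which visit, or how several lesions in one person are combined.

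**The concern.** A between-group test compares the mean or proportion in one set of people with that in another. Outcomes 3 and 4 ask how far the same person's score moves from baseline. With one set of people there is nothing for the named tests to compare, and if subgroups were formed the tests would answer a different question. The plan therefore pre-specifies tests that do not address two of its four outcomes, and no method that does.

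The wound outcomes raise a second, smaller question. If one person can supply several wounds, an interval or test for percent healing might rest on 10 people or on a larger count of correlated wounds, and the plan does not say which. At stake is the validity and pre-specification of any p-value or interval that is reported. The descriptive summaries are not at stake.

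**Working it through.** The plan gives no power, SD, effect size or correlation, so it has no figure to reproduce. The first step is a reading of the text. The others use n = 10 from Sample Size, with any further input marked as assumed.

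**1. Do the named tests match the outcomes?**
- Arms: one, all on the same dressings (Design; Interventions and Interactions).
- Groups defined: none. Demographics, BMI and smoking history are recorded at Visit 1 but are not named as grouping factors.
- Outcomes 3 and 4: change within a person, with scores at baseline and weeks 1, 2, 4 and 8.
- Paired, repeated-measures or mixed-model method named: none.

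The named tests do not estimate outcomes 3 and 4.

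**2. What a paired analysis would give.** The 95% CI half-width for a mean paired change is t(0.975, n−1)/√n, in units of the SD of change. For n = 10 this is 2.262/3.162 = 0.72 SD. If only 8 people complete (assumed), it is 0.84 SD.

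**3. If baseline subgroups were meant.**
- Continuous outcomes, two-sample t-test, two-sided 5% level: a 5 v 5 split needs a difference of 2.02 SD for 80% power, 7 v 3 needs 2.21 SD and 8 v 2 needs 2.53 SD. At a difference of 1 SD, 5 v 5 has 29% power.
- Proportions: the smallest expected count in a 2x2 table is (smaller row total × smaller column total)/10. Each smaller total is at most 5, so the count is at most 5 × 5/10 = 2.5.
- Maximum type I error at nominal 5%, by exact enumeration over a common healing probability from 0.01 to 0.99:

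| Split | Uncorrected chi-square | Continuity-corrected | Fisher |
|---|---|---|---|
| 5 v 5 | 6.2% | 0.2% | 2.1% |
| 4 v 6 | 5.1% | 0.2% | 2.1% |
| 3 v 7 | 6.2% | 0.2% | 1.6% |
| 2 v 8 | 8.7% | 0.7% | 0.7% |

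The uncorrected form can exceed 5%, up to about 9%. The corrected form is very conservative. Fisher's test holds its level and is no more conservative than the corrected form.

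**4. If wounds were treated as independent.** Assume m wounds per person and intraclass correlation ICC; the documents give neither. The design effect is DE = 1 + (m−1) × ICC. The actual error of a nominal 5% one-sample test is approximately 2 × [1 − Φ(1.96/√DE)].
- m = 2, ICC 0.1: DE = 1.1, 1.96/√1.1 = 1.869, error 6.2%. The 20 wounds are worth 20/1.1 = 18.2 independent ones.
- m = 3, ICC 0.3: DE = 1.6, 1.96/√1.6 = 1.550, error 12.1%. The 30 wounds are worth 30/1.6 = 18.8.
- m = 5, ICC 0.5: DE = 3.0, 1.96/√3.0 = 1.132, error 25.8%. The 50 wounds are worth 50/3.0 = 16.7.

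Simulated one-sample t-tests (50,000 runs) give 6.0% and 26.3% at the two extremes. With one mean per person the error is 4.8% to 5.1%.

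**The case against.** The strongest reply is that this is a 10-person case series meant to monitor healing. Descriptive statistics come first and can report the NRS and Sartorius changes. The closing catch-all sentence leaves room for a paired test. No section promises a test or interval for outcomes 3 and 4. Groups formed from baseline factors are also a natural reading, given the data recorded at Visit 1 and the planned regression on predictors. A t-test of change scores between such groups would be valid, though weak.

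Much of this stands, and it limits the point. It would be wrong to say that the plan offers no route to an interval; it offers one that is not pre-specified. What does not fall away is that t-tests and ANOVA are tied in the text to a comparison of groups that are never defined, and that a subgroup comparison would still not estimate the change in the whole series.

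A reader might infer more than the documents support:
- *That visits will be compared as if they were independent groups, or that wounds will be pooled.* The plan says neither. The figures in step 4 show what the open choice could cost, not what is planned.
- *That chi-square would manufacture significant results.* For healing in 0 of 5 v 3 of 5, the uncorrected p is 0.038 against 0.167 by Fisher's test, but the corrected chi-square gives 0.168. The plan does not say which form it means.
- *That percent change is undefined for wounds first seen after baseline.* The plan does not tie percent change to baseline, so change from a wound's first measurement fits the text. The reference visit is simply not stated.

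**Conclusion.** The point holds in a limited form and should be fixed. The mismatch between the named tests and outcomes 3 and 4 follows from the text alone and needs no assumption. The bound of 2.5 on the smallest expected count needs only n = 10. The power figures assume normal data and a chosen split, and the 6% to 26% error range assumes 2 to 5 wounds per person and an ICC of 0.1 to 0.5.

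The practical consequence is modest: the summaries of healing, pain and Sartorius score stay valid whatever is done about the tests. The unit of analysis and the reference visit are open choices, and are secondary to the missing within-person method.

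**What to change.** Delete the sentence on comparing groups, or limit it to named baseline subgroups, labelled exploratory, analysed at person level, with Fisher's exact test for proportions. Put in its place wording such as:

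*Change from baseline in NRS and Sartorius score will be estimated within participant as the mean paired difference with 95% CI (paired t-test, with Wilcoxon signed-rank as a check). Any interval or test for percent change in wound area will use one summary value per participant, or a method that accounts for several wounds per participant. Wounds first seen after baseline will be summarised separately, measured from their first visit.*

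The cost is analysis wording only. It needs no further participants, visits or measurements. Intervals for percent change in area will be wider than those from wounds treated as independent, because they reflect 10 people.

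### The planned regression for independent outcome predictors has only 10 participants, no cap on its terms and no exploratory label (minor)

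*Combined protocol and SAP*

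**What the plan says.** The study is a single-center case series with one treated group. The Objective reads "The objective of this case series is to monitor time and outcome of healing of wounds associated with HS" with the named dressings. The Sample Size entry, under the selection criteria, says "10 participants will be provided with wound care dressings from Appulse Medical" and gives no rationale for that number.

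The Analytical Plan begins with "Results will be analyzed initially using descriptive statistics", moves on to group comparisons, and then commits to the regression: "Regression analysis will be performed to identify independent outcome predictors". It does not state the outcome to be regressed, the type of model, the candidate factors, a maximum number of terms, or whether the unit is the participant or the wound.

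Several candidates will be on file. At Visit 1, "Basic demographics, BMI, and smoking history will be recorded", and the pain scale, DLQI and Sartorius score are completed. At Visits 2 to 5, "Previous and new wounds will be measured", so a participant may contribute more than one wound. The documents do not say how many.

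The plan uses the language of post hoc exploration once, for psychosocial self-report against healing time. The regression is a separate sentence without that label.

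**The concern.** The stated aim is to identify predictors that hold independently of one another. That needs a model with at least two terms, and 10 participants carry little information for one. Three things follow for factors that take one value per person:

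- The model explains a good part of the outcome by chance, and more with each added term.
- A real association of conventionally large size is more likely to be missed than found, so a non-significant factor cannot be ruled out.
- An association that does reach significance is, on average, overstated.

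The plan says that results will be presented or published. At stake is a published statement that some patient factor independently predicts healing, resting on 10 people and not marked as exploratory. The main purpose of the study is not at stake: the descriptive summaries of healing, pain and Sartorius score do not depend on this model.

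**Working it through.** **No figure to reproduce.** The documents give no alpha, power, effect size or rationale for 10, so the check asks what a regression on 10 participants can deliver.

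**Input from the documents.** n = 10 (Sample Size).

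**Assumptions, none in the documents.** Linear model; one fully observed value per participant (percent healing or a score change, not a healing time censored at week 8); no dropout; two-sided 0.05; k terms; effect size f2 on the participant-level outcome. Two and three terms are shown because two is the fewest that the word independent allows; one term is the comparator.

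**Step 1. Chance fit.** Residual df = n − 1 − k = 9 − k. If every predictor is noise, expected R-squared = k/(n − 1) = k/9.

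**Step 2. Hurdle for significance.** A coefficient is significant only if its sample partial correlation exceeds t/√(df + t²) in absolute value, where t is the two-sided 5% critical value.

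- k = 1: 2.306/√(8 + 2.306²) = 0.63
- k = 2: 2.365/√(7 + 2.365²) = 0.67
- k = 3: 2.447/√(6 + 2.447²) = 0.71

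**Step 3. Power.** With predictor values taken as fixed, power comes from the noncentral F(1, df) with noncentrality 10 × f2. At f2 = 0.35 that is 3.5, and the true partial correlation is √(0.35/1.35) = 0.51. With predictors sampled from a normal distribution, power was simulated.

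**Step 4. Exaggeration.** The same simulation gives the mean of |estimate|/truth among results with p < 0.05.

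| | k = 1 | k = 2 | k = 3 |
|---|---|---|---|
| Residual df | 8 | 7 | 6 |
| Expected R-squared from noise | 0.11 | 0.22 | 0.33 |
| Power at f2 = 0.35, fixed predictors | 38% | 37% | 35% |
| Power at f2 = 0.35, sampled predictors | 34% | 30% | 26% |
| Mean exaggeration at f2 = 0.35 | 1.5 | 1.6 | 1.7 |

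At f2 = 0.35, 9% of significant coefficients at k = 2 and 8% at k = 3 are smaller than the truth. Overstatement is thus the usual result, not a certain one.

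**Step 5. Other effect sizes, k = 2 and k = 3.**

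- f2 = 0.15: fixed power 19% and 18%; exaggeration 2.2 and 2.3.
- f2 = 0.70: fixed power 62% and 60%; exaggeration 1.3 and 1.3.
- Fixed power of 80% needs f2 of 1.07 and 1.13, a true partial correlation of 0.72 and 0.73.

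**Step 6. Several wounds per participant.** BMI and smoking still take 10 values, so residual df and noise R-squared do not change. Averaging m wounds does cut outcome noise. If f2 = 0.35 holds per wound, the effective f2 is 0.35/(ICC + (1 − ICC)/m), with m and ICC assumed. Fixed power at k = 2 becomes:

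- m = 2, ICC 0.5: f2 0.47, power 46%
- m = 3, ICC 0.3: f2 0.66, power 60%
- m = 5, ICC 0.1: f2 1.25, power 86%

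**Step 7. The single-factor alternative.** By Fisher's z with n = 10, an observed r of 0.51 has limits tanh(atanh(0.51) ± 1.96/√7), or −0.18 to 0.86.

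**The case against.** The strongest reply is that the harm is blamed on the wrong thing. Moving from two terms to one changes fixed power at f2 = 0.35 only from 37% to 38% and exaggeration from 1.6 to 1.5. That stands. At two terms, low power and overstatement come almost wholly from the sample size, and a single-factor model does not cure them. What does grow with the number of terms is the chance fit.

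The second reply is that the number of terms is unknown. That also stands. A reader might infer from the list of baseline measurements that five or more factors will be entered and the model hopelessly overfitted. The documents name no covariates, so only two terms follow from the wording; beyond that one can say only that noise R-squared rises by 1/9 for each term added.

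Third, the residual df limit of 9 − k binds only participant-level factors. Predictors that vary by wound or visit, such as lesion size or time, have more observations behind them. This stands too, but such a model must account for clustering within participants, and the plan does not provide for it.

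Fourth, a case series is exploratory by nature and descriptive statistics come first. This carries less weight. Coming first sets an order, not a limit, and the plan keeps its exploratory wording for a different analysis.

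A reader might also cite the risk of a false predictor, about 9% to 12% with two or three noise terms, as evidence of overfitting. It is not: it reflects testing several coefficients. Independent 5% tests would give 1 − 0.95² = 9.8% and 1 − 0.95³ = 14.3% at any sample size.

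**Conclusion.** The concern holds at minor severity. The plan commits to identifying independent predictors with 10 participants, without a cap on terms or an exploratory label. For participant-level factors and the smallest models that fit the wording, noise alone yields an expected R-squared of 0.22 to 0.33. Fixed power for an effect of f2 = 0.35 is 35% to 37%, and significant coefficients average 1.6 to 1.7 times the truth. These figures rest on the assumed linear model, effect size, alpha and complete data listed above. Under favorable assumptions about the number of wounds and their correlation, power could be considerably higher.

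A reader might go further and conclude that the design cannot support any predictor analysis. The documents do not support that: the unit of analysis and the number of terms are open, and wound-level or visit-level predictors are not held to 9 − k df. What 10 participants cannot support is a reliable claim of independent participant-level predictors. The severity is minor because the regression belongs to neither the Objective nor the four Outcome Measures, no success criterion hangs on it, and the descriptive results stand without it.

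**What to change.** Replace the regression sentence in the Analytical Plan with:

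> Exploratory regression will estimate the association of a pre-named healing outcome with pre-named baseline factors, one factor per model, each reported with a 95% CI and accounting for clustering of wounds within participants; no independent predictors will be claimed.

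The choice of healing outcome stays with the study team, provided that it is named before analysis.

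The change costs one sentence and leaves visits, data collection and sample size as they are. The team gives up a multivariable predictor claim that 10 participants cannot support. Single-factor estimates will still be imprecise, as the interval of −0.18 to 0.86 in Step 7 shows. The gain therefore lies in dropping the claim, limiting the terms and showing the uncertainty, not in added power.
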